18.2 Informed consent

In seeking and documenting informed consent, the investigator must comply with applicable regulatory requirement(s) and adhere to ICH GCP¹ and the requirements in the Declaration of Helsinki².

Before any trial-related activity, the investigator must give the subject verbal and written information about the trial and the procedures involved in a form that the subject can read and understand.

The subjects must be fully informed of their rights and responsibilities while participating in the trial as well as possible disadvantages of being treated with the trial products.

The investigator must ensure that the subject has ample time to come to a decision whether or not to participate in the trial and before obtaining a voluntary, signed and personally dated informed consent from the subject.

The responsibility for seeking informed consent must remain with the investigator, but the investigator may delegate the task to a medically qualified person, in accordance with local requirements. The written informed consent must be signed and personally dated by the person who seeks the informed consent.

If information becomes available that may be relevant to the subject's willingness to continue participating in the trial, the investigator must inform the subject in a timely manner, and a revised written subject information must be provided and a new informed consent must be obtained.

In this trial additional informed consent must be obtained if:

- A female subject becomes pregnant during the trial, the male partner should be asked to sign a separate informed consent form if an abnormality is found in the foetus or new-born infant.

18.3 Data handling

If the subject withdraws from the trial or is lost to follow-up, then the subject's data will be handled as follows:

- Data already collected and any data collected at the end of trial will be retained by Novo Nordisk, entered into the database and used for the clinical trial report.
- Safety events will be reported to Novo Nordisk and regulatory authorities according to local/national requirements.

If data is used, it will always be in accordance with local regulations and IRBs.

18.4 Information to subjects during trial

The subject may receive information provided to the site by Novo Nordisk, an example of this may be a "thank you for your participation letter" after completion of the trial. Further the subject may receive letters during the trial.

All written information to subjects must be sent to IRB for approval/favourable opinion and to regulatory authorities for approval or notification according to local regulations.

18.5 Premature termination of the trial and/or trial site

Novo Nordisk, the IRBs or a regulatory authority may decide to stop the trial, part of the trial or a trial site at any time, but agreement on procedures to be followed must be obtained.

If the trial is suspended or prematurely terminated, the investigator must inform the subjects promptly and ensure appropriate therapy and follow-up. The investigator and/or Novo Nordisk must also promptly inform the regulatory authorities and IRBs and provide a detailed written explanation.

If, after the termination of the trial, the benefit-risk analysis changes, a new evaluation must be provided to the IRBs in case it has an impact on the planned follow-up of subjects who have participated in the trial. If it has an impact, the actions needed to inform and protect the subjects should be described.

19 Protocol compliance

19.1 Protocol deviations

Deviations from the protocol should be avoided.

If deviations do occur, the investigator must inform the monitor and the implications of the deviation must be reviewed and discussed.

Deviations must be documented and explained in a protocol deviation by stating the reason, date, and the action(s) taken. Some deviations, for which corrections are not possible, can be acknowledged and confirmed via edit checks in the eCRF or via listings from the trial database.

Documentation on protocol deviations must be kept in the investigator trial master file and sponsor trial master file.

19.2 Prevention of missing data

The importance of subject retention will be addressed by Novo Nordisk in the training and communication with the trial sites. Moreover, the subjects will be carefully informed about the trial procedures by the investigator before signing informed consent, so that they know the implications of participating in the trial (see [8.1.3](#)).

The investigator will make every effort to ensure that all assessments are performed and data are collected. If missing data does occur the reason will be collected via the protocol deviation process, see section [19.1](#) Novo Nordisk will monitor protocol deviations on an on-going basis throughout the trial followed by appropriate actions (e.g. re-training of site staff).

20 Audits and inspections

Any aspect of the clinical trial may be subject to audits conducted by Novo Nordisk or inspections from domestic or foreign regulatory authorities or from IRBs. Audits and inspections may take place during or after the trial. The investigator and the site staff as well as Novo Nordisk staff have an obligation to cooperate and assist in audits and inspections. This includes giving auditors and inspectors direct access to all source documents and other documents at the trial site relevant to the clinical trial. This includes permission to examine, analyse, verify and reproduce any record(s) and report(s) that are relevant to the evaluation of the trial.

21 Critical documents

Before a trial site is allowed to start screening subjects, written notification from Novo Nordisk must be received and the following documents must be available to Novo Nordisk:

- Regulatory approval and/or acknowledgement of notification as required
- Approval/favourable opinion from IRBs clearly identifying the documents reviewed as follows: protocol, any protocol amendments, subject information/informed consent form, any other written information to be provided to the subject and subject recruitment materials
- List of IRB members and/or constitution (or a general assurance number/statement of compliance)
- Curricula vitae of investigator and sub-investigator(s) (current, dated and signed - must include documented GCP training or a certificate)
- Signed receipt of IB
- Signed and dated Agreement on Protocol
- Signed and dated Agreement on Protocol Amendment, if applicable
- Contract, signed by the investigator and/or appropriate parties on behalf of the investigator's site and Novo Nordisk
- Source document agreement
- Central laboratory certification and normal ranges
- Insurance statement, if applicable
- Financial disclosure form from investigator and sub-investigator(s)

By signing the protocol agreement, each investigator agrees to comply fully with ICH GCP¹ applicable regulatory requirements and the Declaration of Helsinki².

By signing the protocol agreement, each investigator also agrees to allow Novo Nordisk to make investigator's name and information about site name and address publically available if this is required by national or international regulations.

22 Responsibilities

The investigator is accountable for the conduct of the trial at his/her site and must ensure adequate supervision of the conduct of the trial at the trial site. If any tasks are delegated, the investigator must maintain a log of appropriately qualified persons to whom he/she has delegated specified trial-related duties. The investigator must ensure that there is adequate and documented training for all staff participating in the conduct of the trial. It is the investigator's responsibility to supervise the conduct of the trial and to protect the rights, safety, and well-being of the subjects.

A qualified physician, who is an investigator or a sub-investigator for the trial, must be responsible for all trial-related medical decisions.

The investigator will follow instructions from Novo Nordisk when processing data.

The investigator is responsible for filing essential documents (i.e. those documents which individually and collectively permit evaluation of the conduct of a trial and the quality of the data produced) in the investigator trial master file. The documents including the subject identification code list must be kept in a secure locked facility, so no unauthorized persons can get access to the data.

The investigator will take all necessary technical and organisational safety measures to prevent accidental or wrongful destruction, loss or deterioration of data. The investigator will prevent any unauthorised access to data or any other processing of data against applicable law. The investigator must be able to provide the necessary information or otherwise demonstrate to Novo Nordisk that such technical and organisational safety measures have been taken.

During any period of unavailability, the investigator must delegate responsibility for medical care of subjects to a specific qualified physician who will be readily available to subjects during that time.

If the investigator is no longer able to fulfil the role as investigator (e.g. if he/she moves or retires), a new investigator will be appointed in consultation with Novo Nordisk.

The investigator and other site personnel must have sufficient English skills according to their assigned task(s).

23 Reports and publications

The information obtained during the conduct of this trial is considered confidential, and may be used by or on behalf of Novo Nordisk for regulatory purposes as well as for the general development of the trial product. All information supplied by Novo Nordisk in connection with this trial shall remain the sole property of Novo Nordisk and is to be considered confidential information.

No confidential information shall be disclosed to others without prior written consent from Novo Nordisk. Such information shall not be used except in the performance of this trial. The information obtained during this trial may be made available to other physicians who are conducting other clinical trials with the trial product, if deemed necessary by Novo Nordisk. Provided that certain conditions are fulfilled, Novo Nordisk may grant access to information obtained during this trial to researchers who require access for research projects studying the same disease and/or trial product studied in this trial.

Novo Nordisk may publish on its clinical trials website a redacted clinical trial report for this trial.

One investigator will be appointed by Novo Nordisk to review and sign the clinical trial report (signatory investigator).

23.1 Communication of results

Novo Nordisk commits to communicating, and otherwise making available for public disclosure, results of trials regardless of outcome. Public disclosure includes publication of a paper in a scientific journal, abstract submission with a poster or oral presentation at a scientific meeting, or disclosure by other means.

The results of this trial will be subject to public disclosure on external web sites according to international and national regulations, as reflected in the Novo Nordisk Code of Conduct for Clinical Trial Disclosure¹⁴.

Novo Nordisk reserves the right to defer the release of data until specified milestones are reached, for example when the clinical trial report is available. This includes the right not to release the results of interim analyses, because the release of such information may influence the results of the entire trial.

At the end of the trial, one or more scientific publications may be prepared collaboratively by the investigator(s) and Novo Nordisk. Novo Nordisk reserves the right to postpone publication and/or communication for up to 60 days to protect intellectual property.

In all cases the trial results will be reported in an objective, accurate, balanced and complete manner, with a discussion of the strengths and limitations. All authors will be given the relevant statistical tables, figures, and reports needed to evaluate the planned publication. In the event of any disagreement on the content of any publication, both the investigators' and Novo Nordisk opinions will be fairly and sufficiently represented in the publication.

Where required by the journal, the investigator from each trial site will be named in an acknowledgement or in the supplementary material, as specified by the journal.

Novo Nordisk maintains the right to be informed of plans by any investigator to publish and to review any scientific paper, presentation, communication or other information concerning the investigation described in this protocol. Any such communication must be submitted in writing to Novo Nordisk before submission for comments. Comments will be given within four weeks from receipt of the planned communication.

23.1.1 Authorship

Authorship of publications should be in accordance with the Uniform Requirements of the International Committee of Medical Journal Editors³³ (sometimes referred to as the Vancouver Criteria).

Publication(s) will be prepared for submission to scientific congresses and peer-reviewed journals in collaboration between Novo Nordisk and investigator(s) appointed by Novo Nordisk. These investigator(s) must meet the International Committee of Medical Journal Editors authorship criteria to be named authors on publications.

23.1.2 Site-specific publication by investigator

For a multi-centre clinical trial, analyses based on single-site data usually have significant statistical limitations and frequently do not provide meaningful information for healthcare professionals or subjects, and therefore may not be supported by Novo Nordisk. It is a Novo Nordisk policy that such individual reports do not precede the primary manuscript and should always reference the primary manuscript of the trial.

Novo Nordisk reserves the right to prior review of such publications. Further to allow for the primary manuscript to be published as the first, Novo Nordisk asks for deferment of publication of individual site results until the primary manuscript is accepted for publication. As Novo Nordisk wants to live up to the industry publication policy, submission of a primary publication will take place no later than 18 months after trial completion.

23.2 Investigator access to data and review of results

As owner of the trial database, Novo Nordisk has the discretion to determine who will have access to the database.

Individual investigators will have their own research subjects' data, and will be provided with the randomisation code after results are available.

24 Retention of clinical trial documentation

24.1 Retention of clinical trial documentation

Subject's medical records must be kept for the maximum period permitted by the hospital, institution or private practice.

The investigator must agree to archive the documentation (this includes both electronic and paper-based records) pertaining to the trial in an archive after completion or discontinuation of the trial if not otherwise notified. The investigator should not destroy any documents without prior permission from Novo Nordisk. If the investigator cannot archive the documents at the trial site, Novo Nordisk can refer the investigator to an independent archive provider that has a system in place to allow only the investigator to access the files.

The investigator must be able to access his/her trial documents without involving Novo Nordisk in any way. Site-specific CRFs and other subject data (in an electronic readable format or as paper copies or prints) will be provided to the investigator before access is revoked to the systems and/or electronic devices supplied by Novo Nordisk. These data must be retained by the trial site. If the provided data (e.g. the CD-ROM) is not readable during the entire storage period, the investigator can request a new copy. A copy of all data will be stored by Novo Nordisk.

Novo Nordisk will maintain Novo Nordisk documentation pertaining to the trial for at least 20 years after discontinuation of the marketing authorisation, termination of the trial or cancellation of the research project whichever is longest.

The files from the trial site/institution must be retained for 15 years after end of trial as defined in Section 7, or longer if required by local regulations or Novo Nordisk. In any case trial files cannot be destroyed until the trial site/institution is notified by Novo Nordisk. The deletion process must ensure confidentiality of data and must be done in accordance with local regulatory requirements.

25 Institutional Review Boards and regulatory authorities

25.1 Institutional Review Boards

Written approval or favourable opinion must be obtained from IRB prior to commencement of the trial.

During the trial, the investigator or Novo Nordisk, as applicable, must promptly report the following to the IRB, in accordance with local requirements: updates to IB, unexpected SAEs where a causal relationship cannot be ruled out, protocol amendments according to local requirements, deviations to the protocol implemented to eliminate immediate hazards to the subjects, new information that may affect adversely the safety of the subjects or the conduct of the trial (including new benefit-risk analysis in case it will have an impact on the planned follow-up of the subjects), annually written summaries of the trial status, and other documents as required by the local IRB.

The investigator must ensure submission of the clinical trial report synopsis to the IRB according to local regulatory requirements.

Protocol amendments must not be implemented before approval or favourable opinion according to local regulations, unless necessary to eliminate immediate hazards to the subjects.

The investigator must maintain an accurate and complete record of all submissions made to the IRB. The records must be filed in the investigator trial master file and copies must be sent to Novo Nordisk.

Appendix A

Insulin Titration Guideline

Trial ID: NN9068-4184

DUAL™ II Japan

A double-blinded trial comparing the efficacy and safety of insulin degludec/liraglutide and insulin degludec both in combination with metformin in Japanese subjects with type 2 diabetes mellitus inadequately controlled with basal or pre-mix/combo insulin therapy and oral anti-diabetic drugs

Trial Phase: 3a

Table of Contents

	Page
Table of Contents	2
List of in-text tables	2
1 Introduction	3
2 Treatment regimens	4
2.1 Injection area.....	4
2.2 Time of injection.....	4
3 Initiation and titration	5
3.1 Initiation of IDegLira.....	5
3.2 Initiation of IDeg.....	5
3.3 Titration of IDegLira and IDeg.....	5
3.4 Deviations from the algorithm.....	6
4 Data collection	7
5 Review procedure	8
6 References	9

List of in-text tables

	Page
Table 1 Twice weekly titration on fixed days (Tue/Fri).....	5
Table 2 Twice weekly adjusted titration.....	6

1 Introduction

The goal of insulin therapy is to achieve near normoglycaemia, i.e. to reach a pre-defined HbA_{1c} level with a low rate of hypoglycaemic episodes and as little weight gain as possible. Several trials have shown that this is difficult to achieve, unless plasma glucose values are intensively monitored and the insulin dose(s) frequently adjusted (1-4).

To ensure treatment uniformity between the sites, as well as to ensure that subjects receive an optimal treatment, titration algorithms have been developed specifying recommended dose adjustments at different plasma glucose levels.

It is recognised that treatments differ between different regions and countries. Likewise, specific titration guidelines may not be applicable in certain clinical situations. It is important that other information, such as symptoms of hypo/hyperglycaemia, previous response to dose adjustments, other glucose measurements and other indicators of the subject's level of glycaemic control, is taken into consideration when decisions on dosing are made. The investigator should always use his clinical judgement to avoid safety hazards. The investigator is responsible for the treatment of the subjects and can therefore overrule the guideline.

To optimise and maintain glycaemic control, the investigator should, throughout the trial be at least in weekly contact with the subjects to assist the subjects in adjusting insulin doses and to ensure the subject's welfare.

2 Treatment regimens

At randomisation all subjects will be randomised in a 1:1 manner into two parallel treatment groups:

- IDegLira once daily
- IDeg once daily

First dosing should take place on the day of randomisation (V2) or on the day following randomisation.

Maximum dose for IDegLira is 50 dose steps.

Maximum dose for IDeg is 50 units.

There are no minimum doses for IDegLira or IDeg.

2.1 Injection area

Both IDegLira and IDeg should be injected subcutaneously into the thigh, upper arm (deltoid region) or the abdomen.

The injection site should remain the same throughout the trial. Rotation of injection sites within a given region is recommended.

2.2 Time of injection

Dosing time can be anytime of the day, but should be approximately on the same time each dosing day throughout the trial.

3 Initiation and titration

3.1 Initiation of IDegLira

The recommended start dose of IDegLira is 10 dose steps (10 units of IDeg and 0.36 mg liraglutide) daily, with the option of choosing up to 16 dose steps (16 units IDeg/0.6 mg liraglutide) at the investigator's discretion.

3.2 Initiation of IDeg

The recommended start dose of IDeg is 10 units, with the option of choosing up to 16 units at the investigator's discretion.

3.3 Titration of IDegLira and IDeg

IDegLira and IDeg will be titrated twice weekly according to a predefined titration algorithm aiming to reach a FPG target of 4.0-5.0 mmol/L (72-90 mg/dL).

The doses of IDegLira or IDeg should be adjusted twice weekly by the subject on fixed days (Tuesdays and Fridays), according to a predefined titration algorithm described in [Table 1](#). The investigator will support titration at all contacts.

Table 1 Twice weekly titration on fixed days (Tue/Fri)

	Sun	Mon	Tue	Wed	Thu	Fri	Sat
SMBG	X ¹	X ¹	X ¹	X ²	X ²	X ²	X ²
Dose titration			Titration ¹			Titration ²	
Dose (D)	D ²	D ²	D ¹	D ¹	D ¹	D ²	D ²

¹ The dose for Tuesday, Wednesday and Thursday will be determined based on the mean pre-breakfast SMBG values, obtained on the last Sunday, Monday and Tuesday.

² The dose for Friday, Saturday, Sunday and Monday will be determined based on the mean pre-breakfast SMBG values, obtained on the last Wednesday, Thursday and Friday.

³ SMBG measurements on Saturdays are not used for titration

Dose adjustment will be based on the mean of three pre-breakfast SMBG values measured on the day of the titration and the two days prior to the titration in accordance with [Table 2](#).

Table 2 **Twice weekly adjusted titration**

Mean pre-breakfast SMBG values		Dose adjustment
mmol/L	mg/dL	Dose steps/units
< 4.0	< 72	-2
4.0-5.0	72-90	0
> 5.0	> 90	+2

If one or more SMBGs values are missing, the adjustment should be performed on the remaining SMBG value(s).

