8.5.7 Hypoglycaemic episodes

Plasma glucose should always be measured and recorded when a hypoglycaemic episode is suspected.

All plasma glucose values:

- ≤ 3.9 mmol/L (70 mg/dL) or
- > 3.9 mmol/L (70 mg/dL) when they occur in conjunction with hypoglycaemic symptoms

should be recorded by the subject. These must be transcribed into the eCRF (hypoglycaemic episode form) throughout the trial from randomisation (V2) to FU (P33).

The record should include the following information:

- Date and time of hypoglycaemic episode
- The plasma glucose level before treating the episode (if available)
- Whether the episode was symptomatic
- Whether the subject was able to treat him/herself (if no, see below)
- Type, date, time and dose of last trial product and OAD administration prior to episode
- Date and time of last main meal prior to episode
- Whether the episode occurred in relation to physical activity
- Any sign of fever or other disease
- Whether the subject was asleep when the episode occurred
 - If yes, whether the symptoms of the episode woke up the subject

If the subject was not able to treat him/herself

The answer to the question: "Was subject able to treat him/herself?" must be answered "No" for an episode requiring assistance of another person to actively administer carbohydrate, glucagon, or take other corrective actions. Plasma glucose concentrations may not be available during an event, but neurological recovery following the return of plasma glucose to normal is considered sufficient evidence that the event was induced by a low plasma glucose concentration¹⁹.

If the question "Was the subject able to treat him/herself?" is answered "No", the following information should be recorded:

- Who assisted in the treatment of the hypoglycaemic episode (i.e. family/friend/co-worker or similar, paramedic, doctor or other, please specify)
- Where the treatment was administered (i.e. at home/at friends/at work or similar, in an ambulance, emergency room/hospital or other, please specify)
- Type of treatment provided by other person (i.e. oral carbohydrates, glucagon, IV glucose or other, please specify)
- Were symptoms alleviated after administration of treatment?
- Factors contributing to the episode (i.e. physical activity, missed meal, diet changed, medication error (i.e. overdose, mix-up between products), miscalculation of trial product dose, other factors not listed, please specify or none)
- Did the subject experience seizure?

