8.7.4 Diaries

At each site visit the subjects will be provided with a new diary. The diary must be collected at the next site visit, and retained at the site as source data. However, after ET (V32), the diary data at the FU contact (P33) will be collected per phone. Consequently, source data from the FU contact (P33) will be the notes written by the investigator in the subject's medical record and based on an interview.

The investigator is only allowed to record the following data in the diary:

- Subject number
- Site contact details
- Time and date of next visit or phone contact
- Prescribed dose of trial product
- Prescribed metformin treatment
- Prescribed diabetes treatment at V32
- Doses and values from SMBG measurements from previous diary, if required to complete next dose adjustment
- Review signature and date

The subject must record the following information in the diary:

- Date and value of the daily pre-breakfast SMBG (see section [8.4.1](#))
- Date, actual clock time and value of the 9-point profile SMBG prior to V2, V18 and V32 (see section [8.4.1.1](#))

- Date and dose of trial product each day
 - Time for the first and the last trial product dose taken when randomised and at ET, respectively
- Hypoglycaemic episodes (see section [8.5.7](#))
- Medical issues
- Changes to concomitant medication (see section [8.3.4](#))
- Changes in total daily dose of metformin (see section [8.3.4.1](#))

If the subject is not able to complete the diary and need assistance from a third party to complete the diary, this must be stated in the subject's medical records.

Based on the values from the SMBG measurements, the investigator/subject will assess whether trial product dose needs adjustment according to the titration guideline ([Appendix A](#)).

The diary must be reviewed by the investigator to ensure that AEs, including medical issues and concomitant medication, are reported (see section [8.3.4](#), [8.5.1](#) and [12.2](#)). In addition, the investigator must ensure that the SMBG measurements are reported as hypoglycaemic episodes if required (see section [8.5.7](#)).

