3.4 Deviations from the algorithm

It is recommended that the algorithm is followed. However, it is also important that the decision to adjust the trial drug doses are based on all relevant information as described in section [3.3](#). A reason for deviating from the algorithm should be entered into the eCRF.

4 Data collection

The following data should be entered into the eCRF within 24 hours (on weekdays) after a site visit/phone contact:

- Pre-breakfast SMBG values measured since last visit/phone contact
- Doses of IDegLira or IDeg taken before and after titration
- Reasons for deviation from the titration algorithms, if applicable
- Hypoglycaemic episodes

5 Review procedure

Surveillance of titration data will be performed centrally by Novo Nordisk in an unbiased manner. It is important that data regarding dose titration is entered into the eCRF within 24 hours (on weekdays). If delays occur, action cannot be taken in due time before the subject's next site visit/phone contact. The aim is to reduce the time periods in which a subject may receive suboptimal treatment.

The data listed in section [4](#) will be reviewed by Novo Nordisk within 24 hours (on weekdays). The reviewer may contact the investigator to get clarification regarding the reason for deviation or to request entry of missing data.

When the investigator receives an inquiry, a response should be received at Novo Nordisk within 24 hours (on weekdays).

During the trial HbA_{1c} will be monitored by Novo Nordisk for additional surveillance of the glycaemic control. Novo Nordisk may be in contact with sites (visit or phone contact) to discuss progress in glycaemic control and titration of individual subjects based on SMBGs and HbA_{1c}. This will be done in an unbiased and whenever possible in a blinded manner.

6 References

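### Appendix A gives the self-titrating subject no low-value rule, so the scored default can be +2 on the day of, or at the next titration after, a pre-breakfast value below 3.1 mmol/L

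*Protocol*

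**What the plan says.** **The algorithm.** Under Appendix A, section 3.3, doses of either product "should be adjusted twice weekly by the subject on fixed days (Tuesdays and Fridays"). The basis is stated as "Dose adjustment will be based on the mean of three pre-breakfast SMBG values measured on the day of the titration" and the two days before it. Table 2 is entered with that mean only: below 4.0 mmol/L gives −2, 4.0–5.0 gives 0, above 5.0 gives +2. A footnote to Table 1 adds that "SMBG measurements on Saturdays are not used for titration". If a reading is missing, the mean is taken over those that remain. No row or footnote deals with a single low value or a hypoglycaemic episode.

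**Who decides.** Protocol 8.7.4 says that "the investigator/subject will assess whether trial product dose needs adjustment according to the titration guideline", and the investigator may enter the prescribed dose in the diary.

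**The safeguards.** Appendix A, section 1 says that symptoms of hypoglycaemia and other glucose measurements should be considered in dosing decisions. It continues: "The investigator should always use his clinical judgement to avoid safety hazards" and "The investigator is responsible for the treatment of the subjects and can therefore overrule the guideline". Contact is at least weekly. Section 3.4 only recommends the algorithm, asks that dose decisions rest on all relevant information, and wants a reason recorded for a deviation. Under section 5 the sponsor reviews SMBG values and hypoglycaemic episodes and may contact sites "to discuss progress in glycaemic control and titration of individual subjects based on SMBGs" and HbA1c.

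**The threshold.** Protocol 17.4.1.2 sets the blood-glucose-confirmed cut-off at 3.1 mmol/L (56 mg/dL), with or without symptoms. Severe or confirmed episodes are a key secondary endpoint (Protocol 1.1).

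**The concern.** A three-day mean can hide one low reading, and the Saturday reading enters no mean at all. A subject who applies Table 2 between contacts can therefore arrive at an insulin increase just after a value that the trial itself counts as hypoglycaemia. Protocol 12.6 warns that recovery may take several hours longer with these products than with other long-acting insulins.

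The existing cautions are general, and the explicit power to overrule belongs to the investigator. The sponsor's review follows data entry, so it comes after an increase made between contacts. Under section 3.4, withholding +2 after a low reading is the act that needs a recorded reason, while taking +2 is compliant.

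What is at stake is the safety of the individual subject, not the validity of the HbA1c comparison.

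**Working it through.** The plan states no figure on this point, so there is none to reproduce. The check applies Tables 1 and 2 as written and then asks how often the situation could arise.

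**1. When is +2 scored despite a low value?** With three readings, +2 needs a sum above 3 × 5.0 = 15.0 mmol/L. If one reading is L, the other two must average more than (15 − L)/2. For L = 2.9 this is 6.05 mmol/L.

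- Low on the titration day: (6.2 + 6.2 + 2.9)/3 = 15.3/3 = 5.1, so +2.
- Low on Saturday: Saturday 2.8, then (5.2 + 5.0 + 5.1)/3 = 15.3/3 = 5.1, so +2 on Tuesday.
- One reading missing: (7.1 + 3.0)/2 = 5.05, so +2.

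**2. Contacts against titrations (flow chart, Protocol section 2).** Weeks 0.5–4 have 8 contacts for 8 titrations. Weeks 5–26 have 22 contacts for 22 × 2 = 44 titrations, or 22/44 = 0.5 per titration. A contact can inform more than one titration, but it cannot anticipate a low reading that comes after it.

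**3. Frequency (all inputs assumed).** The documents give no day-to-day SMBG variability. A closed-loop simulation used 20,000 virtual subjects per scenario, with a start at 10 units, the 50-unit cap and the rules of Tables 1 and 2. Assumptions:

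- starting fasting glucose of mean 8 or 9 mmol/L (SD 1.5, minimum 5);
- a fall of 0.05–0.15, 0.08–0.25 or 0.2–0.5 mmol/L per unit, immediate, with a floor of 3.0;
- independent daily readings, normal or log-normal.

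That makes 2 × 3 × 2 = 12 scenarios per CV. Ranges are the minimum to maximum over scenarios; counts come from unrounded rates.

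| Assumed CV | +2 with a pre-breakfast value < 3.1 since the last titration, per subject in 26 weeks | In 210 subjects | Of these, low on the titration day | Saturday the only low day |
|---|---|---|---|---|
| 15% | 0.01–0.05 | 1–10 | 0–1 | 76–88% |
| 20% | 0.08–0.36 | 18–75 | 2–10 | 49–62% |
| 25% | 0.35–1.12 | 75–235 | 14–42 | 36–49% |

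Over 8 + 44 = 52 titrations, the upper ends are 0.05/52 = 0.1%, 0.36/52 = 0.7% and 1.12/52 = 2.2% of titrations. The CV 25% scenarios imply about 5–20 pre-breakfast readings below 3.1 per subject in 26 weeks, so the top row of frequencies belongs to a population with very frequent fasting lows.

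**4. Effect of a hold on pre-breakfast values.** In the same simulation, 0.01–2.2% of titrations are withheld. The largest effects are +0.024 mmol/L in mean fasting glucose (weeks 23–26), −0.12 unit in dose and +0.16 week to target. Readings below 3.1 fall by 0.1–3.2%. If the rule acted at its maximum in one arm and never in the other, the gap between arms would be at most 0.024 − 0 = 0.024 mmol/L. All three profiles in step 1 move from +2 to 0.

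**The case against.** **The tables are not the whole rule.** Sections 1 and 3.4 of the appendix bring other glucose values and all relevant information into dosing decisions, and neither passage exempts the subject's own decisions. This stands. A reader might infer that the dose is set from the mean alone, and the text does not support that. What remains is that the general caution carries no number a subject can apply.

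**What subjects are told is not shown.** The guideline mostly addresses the investigator, and subjects receive titration instruction and a diary whose content the documents do not give. This also stands. That subjects are told to add 2 units after a low value would be an inference; the documents show only what the tables score.

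**The event is rare, and the upper figures need frequent fasting lows with no intervention.** This is correct, and it is why the point is minor. The simulation also assumes an immediate response, although the flow chart notes cite degludec's long half-life.

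**The Saturday case is defensible.** Three newer readings above target on the same dose are a reasonable basis for an increase. That is fair as glycaemic reasoning, but holding for one titration costs little.

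**A hold could slow the comparator.** An any-time-of-day rule would block a basal increase after a daytime low caused by a missed meal or exercise, and could do so more often on IDeg. This is a good reason to limit the rule to pre-breakfast values and severe episodes.

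**Conclusion.** The point holds as a minor safety improvement. By the tables as written, the scored default for a subject adjusting between contacts can be +2 on the day of, or at the next titration after, a pre-breakfast value below 3.1 mmol/L. The safeguards are real but contain no low-value rule for the subject.

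Frequency rests entirely on assumed SMBG variability: about 0.01–0.05, 0.08–0.36 or 0.35–1.1 times per subject in 26 weeks at a CV of 15, 20 or 25%. The benefit is to the individual; overall, at most about 3% of low readings would be avoided.

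A reader might also infer that the algorithm biases the treatment comparison. The documents do not support that: both arms follow one algorithm under blinding, and no bias is claimed here.

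**What to change.** Add under Table 2: *If any pre-breakfast SMBG since the previous titration (Saturday included) is below 3.1 mmol/L (56 mg/dL), or a severe hypoglycaemic episode has occurred, do not increase the dose at this titration; decreases still apply; this is not a deviation.* Give the sentence in the scheduled titration instruction and apply it identically in both arms. Leave non-fasting, non-severe lows to the judgement described in section 1 of the appendix.

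No new data are needed. Pre-breakfast SMBG is already recorded daily (Protocol 8.4.1), and Protocol 8.5.7 already covers episodes: "Plasma glucose should always be measured and recorded when a hypoglycaemic episode is suspected".

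The costs are a protocol amendment with brief retraining, a departure from a purely mean-based score, at most about 2% of titrations withheld, about +0.02 mmol/L in mean fasting glucose, and possibly slightly more holds in the IDeg arm.

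Editorial only: section 3.4 of the appendix cites section 3.3 for the relevant information; it should cite section 1, where that information is.
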